6.6. Concomitant Medications

Concomitant medications will be coded using GSK Drug coding dictionary, summarized, and listed. The summary of concomitant medications will show the number and percentage of participants taking concomitant medications by Ingredient. Multi-ingredient products will be summarized by their separate ingredients rather than as a combination of ingredients. Anatomical Therapeutic Chemical (ATC) classification Level 1 (Body

System) information will be included in the dataset created but will not appear on the listing or summary.

In the summary of concomitant medications, each participant is counted once within each unique ingredient. For example, if a participant takes Amoxycillin on two separate occasions, the participant is counted only once under the ingredient “Amoxycillin”. In the summary of concomitant medications, the ingredients will be summarized by the base only, using CMBASECD and CMBASE. Note: In order to be considered a concomitant medication, the concomitant medication must have been taken at some point during the on-treatment window.

Blood products or blood supportive care products with onset date within the on-therapy window will be included in the summary tables. The frequency and percentage of subjects using blood products and blood supportive care products after the start of study medication will be provided. Supporting listings will also be provided.

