14.4. Appendix 4: Study Phases and Treatment Emergent Adverse Events

14.4.1. Study Phases

Assessments and events will be classified according to the time of occurrence relative to the start and/or stop date of the study treatment. The earliest and latest exposure treatment start and stop dates will be used to determine whether an assessment or event was pre-treatment, on-treatment or post-treatment. If it is not possible to tell whether an assessment or event was on-treatment or not it will be considered as on-treatment.

Study Phase	Definition
Pre-Treatment	Date \leq Study Treatment Start Date
On-Treatment	Study Treatment Start Date $<$ Date \leq Study Treatment Stop Date + 70 days
Post-Treatment	Date $>$ Study Treatment Stop Date + 70 days

NOTES:

- Time of study treatment dosing and assessments and events should be considered, if collected, then the study phases will be re-defined as following:
Pre-Treatment: Date $<$ Study Treatment Start Date
On-Treatment: Study Treatment Start Date \leq Date \leq Study Treatment Stop Date + 70 days
Post-Treatment: Date $>$ Study Treatment Stop Date + 70 days

Concomitant Medication start and end dates will be assigned to study time periods in relation to first dose of study treatment as defined below. The start date references time flag variables and end date reference time flag variables will be added to the concomitant medication datasets, respectively.

- **Start relative to treatment:** Assign to 'BEFORE' if start date is prior to study treatment start date or if subject has not taken any study treatment or (start date is missing and end date is before study treatment start date). Else assign to 'DURING' if the start date falls into the on-treatment period as defined above or if subject is ongoing (not all study treatment discontinuation records completed) or start date is missing. Else assign to 'AFTER' if start date is after the on-treatment period.
- **End relative to treatment:** Assign to 'BEFORE' if end date is prior to study treatment start date or if subject has not taken any study treatment. Else assign to 'DURING' if start date falls into the on-treatment period or if subject is ongoing (not all study treatment discontinuation records completed) or (end date is missing and start relative to treatment not 'AFTER'). Else assign to 'AFTER' if start date is after the on-treatment period or (end date is missing and start relative to treatment='AFTER').

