Concomitant medication starts relative to treatment and end relative to treatment flags are used to select data to include in the Concomitant Medication summaries as follows:

- **Summary of Concomitant Medications:** This summary will contain medications including those with start date prior to study treatment start date and continue (missing end date or end date after study treatment start date) on therapy. Note that any medications with start date and end date prior to study treatment start date will be excluded. In addition, any medication that was started during post-therapy will be

excluded. Include concomitant medication records where start relative to treatment in ('BEFORE','DURING') and end relative to treatment in ('DURING','AFTER').

- Summary of Concomitant Medications with On-Therapy Onset: This summary will contain medications with start date after study treatment start date. In addition, any medication that was started during post-therapy (see above for definition of post-therapy) will be excluded. Include concomitant medication records where start relative to treatment in ('DURING') and end relative to treatment in ('DURING','AFTER').

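### The SAP's end flag for concomitant medications tests the start date, so coded as written some medications taken on treatment drop out of Table 1.160

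*SAP*

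**What the plan says.** SAP 14.4.1 derives a start flag and an end flag for each concomitant medication.

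- **Start flag.** "Assign to 'BEFORE' if start date is prior to study treatment start date"; otherwise DURING or AFTER, according to where the start date falls. A missing start date gives DURING, unless the end date is before treatment.
- **End flag, BEFORE.** "Assign to 'BEFORE' if end date is prior to study treatment start date or if subject has not taken any study treatment".
- **End flag, DURING.** "Else assign to 'DURING' if start date falls into the on-treatment period or if subject is ongoing", where ongoing means that discontinuation records are incomplete ("if subject is ongoing (not all study treatment discontinuation records completed"). DURING also applies when the end date is missing and the start flag is not AFTER.
- **End flag, AFTER.** "Else assign to 'AFTER' if start date is after the on-treatment period or (end date is missing and start relative to treatment='AFTER".

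The Summary of Concomitant Medications keeps a record only if its start flag is BEFORE or DURING and its end flag is DURING or AFTER. The same section says that the summary includes medications with "start date prior to study treatment start date and continue (missing end date or end date after study treatment start date) on therapy". SAP 6.6 gives the general test: "the concomitant medication must have been taken at some point during the on-treatment window".

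The display is Table 1.160 (SAP 14.12.4). SAP 3.1 and 3.2 plan no interim analysis and one final analysis, after all participants have completed the study.

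**The concern.** Only the BEFORE clause of the end flag looks at the end date. DURING and AFTER look at the start date, and their remaining clauses need an ongoing participant or a missing end date. A medication that began before first dose and has a known later stop date therefore seems to have no category, and the filter removes records without an end flag. That would contradict the section's own account of what the summary contains.

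At stake is the completeness of Table 1.160. The direction is also perverse: recording a stop date removes the medication, while leaving it blank keeps it.

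**Working it through.** There is no planned figure to reproduce. The check applies the start flag, end flag and filter as written to each combination of start and end date, then repeats it with the end date tested in the DURING and AFTER clauses.

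**Setting.** A treated participant, not ongoing, under the date-only phases of SAP 14.4.1: pre-treatment is Date ≤ treatment start; on-treatment is treatment start < Date ≤ treatment stop + 70 days; post-treatment is later.

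| Start | End | Start flag | End flag as written | In table? | End flag, end date tested | In table? |
|---|---|---|---|---|---|---|
| before | before | BEFORE | BEFORE | no | BEFORE | no |
| before | on | BEFORE | none | **no** | DURING | yes |
| before | post | BEFORE | none | **no** | AFTER | yes |
| before | missing | BEFORE | DURING | yes | DURING | yes |
| missing | on | DURING | none | **no** | DURING | yes |
| missing | post | DURING | none | **no** | AFTER | yes |
| on | on | DURING | DURING | yes | DURING | yes |
| on | post | DURING | DURING | yes | AFTER | yes |
| post | post | AFTER | AFTER | no | AFTER | no |

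Four patterns are wrongly excluded as written, and testing the end date restores all four. Medications that ended before treatment or began after the window stay out, as the section intends. The on/post row changes label but not inclusion, because the filter accepts both labels.

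**Does another clause rescue these records?**

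- *Ongoing.* If the participant were ongoing, all four patterns would be flagged DURING and kept. At the single final analysis, with discontinuation records complete, this should apply to no one.
- *Default for timing that cannot be determined.* SAP 14.4.1 treats such cases as on-treatment. In the two started-before rows both dates are known. In the two missing-start rows the start flag is already DURING, and it is the end flag, whose date is known, that fails.
- *Partial dates.* SAP 14.7.2.1 imputes partial stop dates, so they count as recorded and are lost in the same way.

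**Is it a slip or a choice?** Two features of the text point to a slip. As written, no record can have a start flag of BEFORE or DURING with an end flag of AFTER, although the filter allows for it. And in the AFTER clause the missing-end condition adds nothing, because a start flag of AFTER already implies a start date after the period. Both make sense only if the clauses were meant to test the end date.

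**First-dose date.** Under the date-only phases, a medication started on the first-dose date is neither prior to treatment start nor in the on-treatment period. It gets no start flag and stays excluded even after the end rule is corrected. A medication started earlier and stopped on that date likewise still gets no end flag. The timed phases use treatment start ≤ Date and close this gap, but Protocol 6.5 asks for start and end dates of concomitant medication and does not list times. The schedule of activities starts prophylactic artificial tears on Cycle 1 Day 1, so the gap has a practical case if they are recorded as concomitant medication.

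**The case against.** The intended rule is plain from SAP 14.4.1's own description of the summary and from SAP 6.6, so a careful programmer would probably code the end date. The derivation program is not in the documents, and an actual loss is not shown. This stands: the point is what the text yields if followed literally.

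The effect is also bounded. Long-term medications with no stop date are kept. SAP 6.6 counts each participant once per ingredient, so a dropped record changes the table only if that participant has no other qualifying record of the ingredient. Listing 1.070 (prior and concomitant medications) is not described as using these flags. All of this stands.

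A reader might infer that reading of cytopenia, infection or ocular events is compromised. The documents do not support that. SAP 8.2 to 8.5 define the adverse event analyses without concomitant medication, and nothing says that Table 1.160 is used to interpret those events. The obvious drug examples are weak too: artificial tears begin on Cycle 1 Day 1, active infection needing treatment is an exclusion criterion, and chronic oral steroids are prohibited with limited exceptions.

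What remains is that an operational rule and filter contradict the stated content of the table. A validator working from the rule would reproduce the wrong table.

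**Conclusion.** The concern holds as an error in a stated selection rule. Coded literally, it excludes medications that the SAP says belong in Table 1.160: those started before treatment, or with a missing start date, that have a recorded stop date during or after the on-treatment period.

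The consequence is an undercount in one descriptive table. No primary or secondary endpoint is affected. The number of affected records cannot be derived. For scale, Protocol 4.1 plans up to 12 evaluable participants, up to six per cohort. If the table denominator were 12, one participant missing from an ingredient row would move it by 1/12 = 8.3 percentage points; if it were six, by 1/6 = 16.7 points.

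This rests on two assumptions: that the program follows the text, and that discontinuation records are complete at the final analysis. It does not follow that every pre-existing medication is lost, or that the data disappear from the report.

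**What to change.** In SAP 14.4.1, under the end flag, replace the start date by the end date in the first condition of both the DURING and AFTER clauses. Keep the ongoing and missing-date conditions.

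For the two concomitant-medication flags only, define on-treatment as treatment start date ≤ Date, so that medications starting or ending on the first-dose date are flagged when times are not collected. The section's prose speaks of end dates before or after treatment start and leaves that day open, so state the choice. The phase definitions for assessments need not change.

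Then check the derivation program against the corrected text, using the date patterns tabulated above plus the first-dose-date cases. The cost is a few words of SAP text and one program check; no new data are needed.

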14.4.2. Treatment Emergent Flag for Adverse Events

Flag	Definition
Treatment Emergent	
• Study Treatment Start Date ≤ AE Start Date ≤ Study Treatment Stop Date + 70 days.

NOTES:

- If the study treatment stop date is missing, then the AE will be considered to be On-Treatment.
- Time of study treatment dosing and start/stop time of AEs should be considered, if collected.

14.5. Appendix 5: Data Display Standards & Handling Conventions

14.5.1. Reporting Process

Software	

 The currently supported versions of SAS software 9.4 will be used. 	
Reporting Area	
HARP Server	: us 1salx00259
HARP Compound	: GSK2857916/mid208465
Analysis Datasets	

 Analysis datasets will be created according to CDISC standards 	
Generation of RTF Files	

 Rich Text Format (RTF) files will be generated for the final reporting effort for use in writing the CSR. 	

14.5.2. Reporting Standards

General	

 The current GSK Statistical Display Standards in the GSK Standards Library (IDSL) will be applied for reporting, unless otherwise stated (Library Location: https://spope.gsk.com/sites/IDSLLibrary/SitePages/Home.aspx): 
 4.03 to 4.23: General Principles 5.01 to 5.08: Principles Related to Data Listings 6.01 to 6.11: Principles Related to Summary Tables 7.01 to 7.13: Principles Related to Graphics Do not include participant level listings in the main body of the GSK Clinical Study Report. All participant level listings should be located in the modular appendices as ICH or non-ICH listings 	
Formats	

 GSK Statistical Display Principles (5.03 & 6.06.3) for decimal places (DP's) will be adopted for reporting of data based on the raw data collected, unless otherwise stated. Numeric data will be reported at the precision collected on the eCRF. The reported precision from non eCRF sources will follow the GSK Standard Statistical Display Principles but may be adjusted to a clinically interpretable number of DP's. 	
Planned and Actual Time	

 Reporting for tables, figures and formal statistical analyses: 
 Planned time relative to dosing will be used in figures, summaries, statistical analyses and calculation of any derived parameters, unless otherwise stated. The impact of any major deviation from the planned assessment times and/or scheduled visit days on the analyses and interpretation of the results will be assessed as appropriate. Reporting for Data Listings: 
 Planned and actual time relative to study drug dosing will be shown in listings (Refer to GSK Standard Statistical Display Principle 5.05.1). Unscheduled or unplanned readings will be presented within the participant's listings. 	
Unscheduled Visits	

 Unscheduled visits will not be included in summary tables and/or figures that need to be summarized by visits. All unscheduled visits will be included in listings. 	

Descriptive Summary Statistics	
Continuous Data	Refer to GSK Standard Statistical Display Principle 6.06.1
Categorical Data	N, n, frequency, %
Graphical Displays	

 Refer to GSK Standard Statistical Display Principals 7.01 to 7.13. 	

14.5.3. Reporting Standards for Pharmacokinetic

Pharmacokinetic Concentration Data	
PC Windows Non-Linear (WNL) File	PC WNL file (CSV format) for the non compartmental analysis by Clinical Pharmacology Modelling and Simulation function will be created according to Standards for the Transfer and Reporting of PK Data document. Note: Concentration values will be imputed as per GUI_51487
Descriptive Summary Statistics, Graphical Displays and Listings	
Refer to the GSK Standard PK Display Standard.
 
Refer to the GSK Standard Statistical Display Principle 6.06.1.
 
Note: Concentration values will be imputed as per GUI_51487 for descriptive summary statistics/analysis and summarized graphical displays only.

NONMEM/Pop PK File	Not applicable.
NONMEM/PK/PD File	Not applicable.
Pharmacokinetic Parameter Derivation	
PK Parameter to be Derived by Programmer	
The following PK parameter will be derived by the Programmer:
 
 Accumulation ratios based on Cycle 1 and Cycle 4 CEOI and Ctrough values
Pharmacokinetic Parameter Data	
Is NQ impacted PK Parameters Rule Being Followed	Yes, refer to [Standards for Handling NQ Impacted PK Parameters].
Descriptive Summary Statistics, Graphical Displays and Listings	Refer to GSK Standard PK Display Standard.

14.6. Appendix 6: Derived and Transformed Data

14.6.1. General

Multiple Measurements at One Analysis Time Point

 If there are two or more values within a time window (as per Section 14.3) the value closest to the target day for that window will be used for summary tables. If values are the same distance from the target, then the mean will be taken, but if listed, all data will be presented. Participants having both High and Low values for Normal Ranges at any post-baseline visit for safety parameters will be counted in both the High and Low categories of "Any visit post-baseline" row of related summary tables. This will also be applicable to relevant Potential Clinical Importance summary tables.
Study Day

 Calculated as the number of days from First Dose Date: 
 Ref Date = Missing → Study Day = Missing Ref Date < First Dose Date → Study Day = Ref Date – First Dose Date Ref Date ≥ First Dose Date → Study Day = Ref Date – (First Dose Date) + 1

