6.6. Dose Modification

Table 4 details the permitted dose modifications of belantamab mafodotin. Table 5 and Table 6 contain dose modification guidance for drug-related AEs. See Table 7 for dose modification guidelines for belantamab mafodotin treatment-related changes in vision.

Table 4 Permitted Dose Reductions

Starting dose	Dose reduction
2.5 mg/kg	1.9 mg/kg
3.4 mg/kg	2.5 mg/kg, 1.9 mg/kg

If the participant cannot tolerate the drug after the allowed dose reduction of belantamab mafodotin to the lowest allowed dose of 1.9 mg/kg, he or she must discontinue treatment for lack of tolerability.

In case of full resolution of symptoms which lead to dose reduction, further treatment at the previous dose level may be considered by the investigator.

If a dose is delayed, the participant should wait for the next scheduled dose to resume treatment. In individual cases where in the judgment of the Investigator waiting a full cycle to resume treatment after delay (skipping dose) related to toxicity which has resolved would be detrimental to the participant's health, the PI should contact the Medical Monitor to discuss an earlier re-start. An earlier re-start may be considered only for participants who have recovered from toxicity to at least ≤Grade 1. The dosing with belantamab mafodotin cannot occur more frequently than every 21 days (±3-day

window). In such cases, efficacy and safety assessments must remain every 3 weeks in line with initial efficacy and safety assessments on study, which may result in 2 separate visits (1 for dosing, 1 for disease assessments). Evaluations associated with a dose would be entered into the eCRF under the next scheduled cycle.

Resuming treatment with belantamab mafodotin will be possible with or without dose reduction after the toxicity has resolved to Grade 1 or less.

Table 5 Dose Modification Guidelines for Belantamab Mafodotin-Related Adverse Events

Toxicity	Grade/description of toxicity	Recommendations for Belantamab Mafodotin
Elevated serum creatinine which cannot be explained by concomitant sepsis, TLS, other severe condition with fever, or dehydration	If absolute serum creatinine increases from baseline by >0.5 mg/dL	 Repeat serum creatinine within 48 hours If confirmed: withhold therapy, institute treatment and monitoring as clinically indicated, and follow for resolution Discuss any further dosing with Medical Monitora

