9.4.3. Safety Analyses

The All Treated Population will be used for the analysis of safety data (except the DLT analysis). All serially collected safety endpoints will be summarized according to the scheduled, nominal visit at which they were collected and across all on-treatment time points using a "worst-case" analysis. Complete details of the safety analyses will be provided in the Reporting and Analysis Plan (RAP).

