Required Action	Required Actions and Follow up Assessments following ANY Liver Stopping Event			
Ac	ctions	Follow Up Assessments		
Complete the live an SAE data colle meets the criteria Perform liver ever Monitor the partic resolve, stabilise, baseline (see MO Do not restart/re study treatment u and GSK Medical granted (refer to Appendix) If restart/rechaller protocol or not g discontinue study continue participa	to GSK within 24 hours r event CRF and complete action tool if the event also	 Viral hepatitis serology⁴ Only in those with underlying chronic hepatitis B at study entry (identified by positive hepatitis B surface antigen) quantitative hepatitis B DNA and hepatitis delta antibody⁵. Obtain INR and recheck with each liver chemistry assessment until the aminotransferases values show downward trend Blood sample for pharmacokinetic (PK) analysis, obtained within 45 days after last dose⁶ Serum creatine phosphokinase (CPK) and lactate dehydrogenase (LDH), gamma glutamyl transferase [GGT], glutamate dehydrogenase [GLDH], and serum albumin. Fractionate bilirubin, if total bilirubin≥2xULN Obtain complete blood count with differential to assess eosinophilia 		

MONITORING:

If ALT≥3xULN AND total bilirubin ≥2xULN or INR >1.5:

- Repeat liver chemistries (include ALT, AST, alkaline phosphatase, bilirubin) and perform liver event follow up assessments within 24 hrs
- Monitor participants twice weekly until liver chemistries resolve, stabilise or return to within baseline
- A specialist or hepatology consultation is recommended

_For All other criteria (bilirubin <2xULN and INR ≤1.5):

- Repeat liver chemistries (include ALT, AST, alkaline phosphatase, bilirubin) and perform liver event follow up assessments within 24-72 hrs
- Monitor participants weekly until liver chemistries resolve, stabilise or return to within baseline

- Record the appearance or worsening of clinical symptoms of liver injury, or hypersensitivity, on the AE report form
- Record use of concomitant medications on the concomitant medications report form including acetaminophen, herbal remedies, other over the counter medications
- Record alcohol use on the liver event alcohol intake case report form

If ALT ≥3xULN AND total bilirubin ≥2xULN or INR >1.5 obtain the following in addition to the assessments listed above:

- Anti-nuclear antibody, anti-smooth muscle antibody, Type 1 anti-liver kidney microsomal antibodies, and quantitative total immunoglobulin G (IgG or gamma globulins).

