8.7. Clinical Laboratory Analyses

Only local laboratory evaluations including the analyses of Chemistry laboratory tests, Haematology laboratory tests, Urinalysis, and liver function tests will be based on GSK Core Data Standards. The details of the planned displays are in [Appendix 12: List of Data Displays](#).

Summaries of worst case grade increase from baseline grade will be provided for all the lab tests that are gradable by CTCAE v5.0. These summaries will display the number and percentage of participants with a maximum post-baseline grade increasing from their baseline grade. Any increase in grade from baseline will be summarized along with any increase to a maximum grade of 3 and any increase to a maximum grade of 4. Missing baseline grade will be assumed as grade 0. For laboratory tests that are graded for both low and high values, summaries will be done separately and labelled by direction, e.g., sodium will be summarized as hyponatremia and hypernatremia.

Separate summary tables for haematology, and chemistry laboratory tests will be produced. Liver function laboratory tests will be included with chemical chemistry.

A supporting listing of laboratory data for subjects with abnormalities of potential clinical concern will be provided. A separate listing of laboratory data with character values will also be provided. For lab test values that can be graded, values of grade 1 or above are defined as values of potential clinical concern. For lab test values that cannot be graded, values out of the normal range are defined as values of potential clinical concern.

Detailed derivation of baseline assessment is specified in Section 5.2.

Unless otherwise specified, the denominator in percentage calculation at each scheduled visit will be based on the number of participants with non-missing value at each particular visit.

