14.3. Appendix 3: Assessment Windows

All assessments on study must be performed on a calendar schedule in [Appendix 2: Schedule of Activities](#) and must not be affected by dose interruptions/delays. For post-baseline assessments, a window of ± 3 days is permitted to allow for flexible scheduling, and PD follow-up visits have a ± 7 days window.

For analysis endpoints, the analysis visit will be re-mapped by the assessment time windows. In general, the summary tables will only be displayed by planned time points and visits, unless otherwise specified.

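### SAP 14.6.1's closest-value-or-mean rule is not limited to by-visit tables, so applied literally it can remove the worst value from the worst-grade laboratory and liver tables

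*SAP*

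**What the plan says.** SAP 14.3 (Assessment Windows) states: "For post-baseline assessments, a window of ± 3 days is permitted to allow for flexible scheduling". It adds that "the analysis visit will be re-mapped by the assessment time windows".

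SAP 14.6.1 (General) then deals with two or more values in one window: "the value closest to the target day for that window will be used for summary tables". For ties: "If values are the same distance from the target, then the mean will be taken". Listings keep all values. A second bullet in the same section lets a participant count as both high and low in an any-visit post-baseline row, and extends this to the tables of potential clinical importance.

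SAP 8.7 defines the laboratory tables differently: "Summaries of worst case grade increase from baseline grade will be provided for all the lab tests", taking the highest grade reached after baseline. SAP 8.7.1 adds hepatobiliary events and possible Hy's law cases. Neither section says which records feed the maximum.

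Protocol 9.4.3 requires serially collected safety endpoints to be "summarized according to the scheduled, nominal visit at which they were collected and across all on-treatment time points", the latter as a worst-case analysis. SAP 2.1 declares no change from the protocol's planned analysis.

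**The concern.** Choosing the value nearest the target day is a normal way to fill a by-visit table. It does not suit a table that reports the worst value, because it chooses by date and takes no account of severity. Averaging tied values does not suit it either, since a mean can sit below a threshold that one of its components crossed.

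Change in laboratory parameters is a secondary safety endpoint, in a study of up to 12 evaluable participants whose main purpose is safety. If the rule were programmed as written, the worst-grade and liver tables could show less toxicity than was observed. They would then disagree with the listings and adverse event tables in the same report, and would be an undeclared departure from Protocol 9.4.3. SAP 14.5.2 keeps participant listings out of the main body of the report, so a reader of the body would see only the tables.

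**Working it through.** The plan gives no figure to reproduce here. The check sets the rule against the tables it would govern, then applies it to assumed values.

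**Which tables the rule reaches.** The list of displays in SAP Appendix 12 has three laboratory summary tables: 4.170 (chemistry, worst grade change), 4.180 (haematology, worst grade change) and 4.190 (hepatobiliary abnormalities). It has no by-visit laboratory table. For laboratory data, the summary tables named in 14.6.1 can therefore only be these three. The bullet on any-visit rows confirms that the section extends beyond by-visit displays, but it does not restore a value already dropped within a window.

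**Whether two values can share a window.** The window runs from 3 days before target to 3 days after. Protocol Table 5, for a creatinine rise above 0.5 mg/dL, says "Repeat serum creatinine within 48 hours". Protocol Appendix 5, after a liver stopping event with bilirubin <2xULN and INR ≤1.5, says "perform liver event follow up assessments within 24-72 hrs". If the first sample is on the target day, both kinds of repeat fall inside the window, and the first sample is nearer the target.

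**The rule applied.** Let d be days from target. The rule keeps the value with the smallest |d|, or the mean if |d| is tied. The worst-case value is the maximum (the minimum for blood counts). All laboratory values below are assumed; the thresholds are the protocol's (Appendix 5 for liver, Table 5 for neutrophils).

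| Values | d | Rule gives | Worst | Threshold |
|---|---|---|---|---|
| ALT 2.8, 5.6xULN | 0, +2 | 2.8 | 5.6 | ≥5 |
| ALT 2.8, 5.6xULN | −1, +1 | (2.8+5.6)/2 = 4.2 | 5.6 | ≥5 |
| ALT 2.4, 3.4xULN | −1, +1 | (2.4+3.4)/2 = 2.9 | 3.4 | ≥3, jointly with bilirubin |
| Bilirubin 1.5, 2.3xULN (same samples) | −1, +1 | (1.5+2.3)/2 = 1.9 | 2.3 | ≥2, jointly with ALT |
| Neutrophils 0.7, 1.5 x10^9/L | −1, +1 | (0.7+1.5)/2 = 1.1 | 0.7 | <1.0 |

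Every threshold crossing is lost. The bilirubin example assumes that more than 35% is direct.

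In the ALT rows, the first value (2.4 or 2.8xULN) would not itself trigger a mandated repeat. Those repeats would be discretionary, as Protocol Section 8 allows for safety reasons. A case driven by the protocol is as follows. Cycle 3 Day 1 is Day 1 + 2×21 = 43, so its window is Days 40 to 46. ALT of 5.5xULN with bilirubin of 1.6xULN on Day 43 is a stopping event. The 24-72 hour repeat falls on Days 44 to 46, inside the window. If it shows bilirubin of 2.3xULN with ALT still ≥3xULN, the rule keeps Day 43, and the possible Hy's law combination does not reach Table 4.190.

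**Direction.** A selected value or a mean can never be more extreme than the worst value. Any error therefore understates severity.

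**Size.** One participant is 100/6 = 16.7 percentage points of a cohort of 6, or 100/12 = 8.3 points of 12. The loss changes a table only if no retained value at another visit shows the same or a worse grade.

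**The case against.** The strongest reply is that the SAP as a whole points to using every value. The rule's title concerns one analysis time point. SAP 14.3 says tables are displayed by planned visit unless otherwise specified, and a maximum post-baseline grade is such a specification. SAP 14.5.2 drops unscheduled visits only from tables summarised by visit, a limit with little purpose if repeats were already removed everywhere. The sponsor's display standards and mock shells, which are not in these documents, may settle the matter.

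This stands as evidence of intent. It does not remove the conflict: 14.5.2 contains a by-visit limit and 14.6.1 does not. SAP 5.2 expressly admits unscheduled values for baseline, and no matching sentence covers the post-baseline worst case.

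The consequence is also limited. The primary endpoints (DLTs and adverse events) do not use the rule. The combined ALT and bilirubin event must be reported as a serious adverse event. Listing 1.221 shows all laboratory data for any participant with a value of potential clinical importance.

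Three stronger readings are tempting, but the documents do not support them:

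- A reader might infer that mid-cycle values are lost because the windows cover only part of each cycle from Cycle 2. SAP 14.6.1 only chooses among values inside a window; it does not delete values outside every window.
- A reader might infer that any raised ALT creates a quick repeat in the same window. Appendix 5 prescribes weekly tests for ALT of 3 to <5xULN without symptoms and with bilirubin <2xULN, and a test a week after the target day falls outside the window.
- A reader might want a rate of lost Grade 4 platelet counts. Table 5 requires no repeat count for thrombocytopenia, and the documents give no within-patient variability, so any rate would rest on assumptions alone.

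**Conclusion.** The point holds as a conflict in the text with a one-directional consequence. SAP 14.6.1 states a rule for summary tables without limit. Followed literally, it can drop or average away the worst value that SAP 8.7 and Protocol 9.4.3 require in Tables 4.170, 4.180 and 4.190. It does not show that values will be lost, since the authors probably meant all of them to count.

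Each missed participant costs 16.7 points of 6 or 8.3 points of 12. The frequency cannot be estimated from the documents. The conclusion assumes literal programming of 14.6.1 and no overriding instruction in the display standards that were not available. The ECG tables carry less risk, because no rule prompting repeat QTc readings was identified; they are included in the fix for consistency.

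**What to change.** In SAP 14.6.1, limit the closest-to-target and mean-if-tied rule to by-visit summaries. Then add: worst-case post-baseline displays (Tables 4.170, 4.180, 4.190, the worst-case part of 4.200, and 4.210) use every on-treatment value, including repeat and unscheduled values, with no selection or averaging other than the mean of a planned ECG triplicate.

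This costs one short SAP edit and needs no new data. The downside is that some worst-grade counts may be slightly less favourable than under the literal rule.
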